### **10 Study Procedures**

#### **10.1 Subject Recruitment and Screening**

Patients will be recruited at the study centers during preoperative visits through normal referral patterns. All patients recruited for this study will have the capacity to give informed consent. Advertising for the study at each center will be at the discretion of the investigator. All handouts, brochures, advertisements, etc. must be approved by the IRB/EC prior to the dissemination of any recruitment materials to potential subjects.

#### **10.2 Patient Informed Consent and Guidelines**

All patients for this study will be provided an Informed Patient Consent Form describing this study and providing sufficient information for them to make an informed decision about their participation. The Informed Patient Consent Form must contain all elements required by the FDA under 21 CFR Part 50, in addition to any other elements required by state, local and institutional policies. See Appendix E for a copy of the Model Informed Patient Consent. This will be submitted with the protocol for review and approval by the IRB for the study. All patients must provide written consent after having had adequate time to consider their participation in the study. The formal consent of a patient, using the IRB approved Informed

CONFIDENTIAL

This material is the property of Stryker Spine. Do not disclose or use except as authorized in writing by Stryker.  
Page 28

Patient Consent Form, must be obtained before that patient is submitted to any protocol related procedures that are not part of normal care. Written documentation of consent must be provided on the Informed Patient Consent Form's signature page in addition to a note in the patient medical records indicating the date that consent was obtained. The investigator-designated research professional obtaining the consent must also sign this Informed Patient Consent Form. The patient or his/her legal representative should receive a signed copy of the Informed Patient Consent Form, according to GCP guidelines.

The procedure for obtaining informed consent is outlined below:

- Use a current IRB approved copy of the Informed Patient Consent Form.
- Review thoroughly with the patient before having them sign.
- After the patient has consented to the procedures, ensure he/she signs and dates the Informed Patient Consent Form.
- The person obtaining consent also signs and dates the signature page.
- Provide a copy of the Informed Patient Consent Form to the patient.
- If required, provide the hospital with a copy of the signed Informed Patient Consent Form.
- Maintain the signed original in the patient's study chart.

## 10.3 Early Withdrawal of Subjects

### *When and How to Withdraw Subjects*

In the event that the subject is discontinued by the investigative center prior to the final study evaluation, the subject will be notified by the center that he/she is no longer in the study and a Study Termination CRF will be completed.

The following is a list of reasons for which subjects may be withdrawn and the date of termination that should be used on the Study Termination CRF in each situation. This list is not all inclusive:

Termination Reason	Date of Termination
Death	Date of death
Investigative center termination	Date of study close-out visit
Lost to follow-up	Date Stryker termination approval given
Voluntary withdrawal	Date subject notified center of withdrawal
Removal of study device	Date of removal procedure
Study device not implanted	Date of surgery
Surgery not performed	Date Stryker termination approval given

At the time of study surgery it is required that the following components are implanted: AccuLIF interbody implant, supplemental fixation via pedicle screws, bone graft (autogenous and / or corticocancellous allograft chips).

CONFIDENTIAL

This material is the property of Stryker Spine. Do not disclose or use except as authorized in writing by Stryker.  
Page 29

Revision or removal of the AccuLIF Cage System constitutes a failure and study termination for the subject.

If revision of supplemental fixation is required during the study, the event is considered a reoperation and does not constitute a failure or study termination.

If the subject fails to return for his/her follow-up appointments, every effort should be made to contact the subject to assess his/her health status. If, after attempting to contact the subject through three documented phone calls and a certified letter, the subject still does not respond, he/she will be considered lost to follow-up. A Study Termination CRF will be completed **only after notifying Stryker of the subject's status and being given approval to terminate.**

In the event a subject does not have surgery, Stryker should be contacted to discuss if/when the surgery will be rescheduled. If the surgery is rescheduled more than 4 months from the date of preoperative data collection, the subject will need to be re-consented, all preoperative data will need to be re-collected and all original preoperative data will need to be removed from the database. If the surgery is not to be rescheduled or if the subject is no longer considered an appropriate study candidate, a Study Termination CRF may be completed **only after notifying Stryker of the subject's status and being given approval to terminate.**

When a subject completes the study according to protocol, including the final study evaluation, a Study Termination CRF will be completed.

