This material is the property of Stryker Spine. Do not disclose or use except as authorized in writing by Stryker.  
Page 11

Ancillary Devices	
The AccuLIF system is indicated for use with autogenous bone and/or allograft (cancellous or corticocancellous allograft chips) and supplemental fixation. Stryker supplementation fixation (Xia or ES2 pedicle screws must be used as part of the study protocol).

Statistical Methodology	
All continuous data will be summarized using continuous descriptive statistics: number of subjects with responses (n), mean, standard deviation, median, minimum, and maximum. Changes from baseline, where appropriate, will be calculated as the follow-up measure minus the baseline measure, where baseline is defined as the last measure prior to the AccuLIF spinal system surgical procedure.
 
All categorical data will be summarized using counts and percentages. Denominators for percentages will be the number of subjects in the respective patient population with nonmissing data.
 
For the primary endpoint of an increase of 3 degrees or more of segmental lordosis, a one-sided analysis (<math>\alpha=0.05</math>) will be used to assess significance. A one-sample t-test will be employed. Although the primary analysis will be at 24 months, similar analyses will be performed at each visit. Both the change from baseline and the results at each visit will be summarized.
 
For all other radiographic parameters, the change from baseline will be analyzed at each visit using two-sided, one-sample t-tests (<math>\alpha=0.05</math>) comparing the change from baseline to 0.
 
Secondary and exploratory endpoints will be analyzed where appropriate. Where changes from baseline can be calculated for numerical data, statistical analyses will be performed. Analyses will follow the two-sided approach taken for the primary analyses. Data that is ordinal in nature, such as the changes in clinical outcomes, may be analyzed using Wilcoxon signed rank tests, comparing baseline measures to follow-up measures. All analyses will be two-sided and evaluated at an alpha level of 0.05.

CONFIDENTIAL

This material is the property of Stryker Spine. Do not disclose or use except as authorized in writing by Stryker.  
Page 12

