## 9 Statistical Plan

### 9.1 Efficacy Parameters

#### 9.1.1 Primary Objective Parameters

The primary objective parameters of this study are the change in pre-operative to post-operative radiographic outcomes of a cohort treated for degenerative disease at one or two levels implanted with the AccuLIF spinal system at one level via TLIF procedure with supplemental fixation. The primary objective will be evaluated at 12 months post-operatively.

Primary Radiographic parameters are defined as:

- Disc height (anterior, middle, posterior in millimeters)
- Foraminal height (in millimeters)
- Segmental lordosis (at each TLIF level in degrees)
- Regional Lordosis: (inferior endplate T12-S1 in degrees)
- Sagittal balance: (C7-S1 in millimeters)

  

- Success is defined as an increase of 3 degrees or more of segmental lordosis 12 months post operatively.

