#### 9.1.2 Primary Objective Hypothesis

Success is defined as an increase of 3 degrees or more of segmental lordosis post operatively. The primary null hypothesis is as follows:

H0: Subjects implanted with the AccuLIF spinal system will have less than 3 degrees increase in segmental lordosis 12 months post-operatively.

H0: Subjects implanted with the AccuLIF spinal system will have an increase of at least 3 degrees in segmental lordosis 12 months post-operatively.

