## 9.3 Missing Data

The primary analyses will be based on observed data. In addition, sensitivity analyses will be performed including missing data using a Markov Chain Monte Carlo multiple imputation method and using the last observation carried forward.

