#### **9.5 Efficacy Patient Population**

All patients enrolled in the study with any follow-up efficacy assessment (radiographic assessment) will be included in the efficacy patient population.

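### Cage revision or removal is declared a failure in 10.3, but Section 9 never uses that status, so a failure before the primary visit drops out of the observed-data result or is treated as ordinary missing data

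*Combined protocol and SAP*

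**What the plan says.** Section 10.3 (Early Withdrawal of Subjects): "Revision or removal of the AccuLIF Cage System constitutes a failure and study termination for the subject". Section 8.5 also refers to individual subject failures, without linking them to an endpoint.

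Section 9 does not mention failure, revision or removal in the success definition, hypotheses, tests, missing-data rule or populations. The rules that apply are:

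- 9.1.1, success: "Success is defined as an increase of 3 degrees or more of segmental lordosis 12 months post operatively".
- 9.1.2, null hypothesis: "Subjects implanted with the AccuLIF spinal system will have less than 3 degrees increase in segmental lordosis 12 months post-operatively".
- 9.3, primary analysis: "The primary analyses will be based on observed data".
- 9.3, other analyses: "sensitivity analyses will be performed including missing data using a Markov Chain Monte Carlo multiple imputation method and using the last observation carried forward".
- Synopsis, Statistical Methodology: "Denominators for percentages will be the number of subjects in the respective patient population with nonmissing data". Section 9.4.1 does not repeat this rule.
- 9.5: "All patients enrolled in the study with any follow-up efficacy assessment (radiographic assessment) will be included in the efficacy patient population".

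The only responder percentage listed in Section 9 is the exploratory composite in 9.1.6.

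**The concern.** The plan makes an outcome judgement about these subjects and then has no place to record it. Because follow-up ends at the failure, the primary-visit value is missing for a reason tied to the device. The observed-data mean then describes subjects whose cage was still unrevised at that visit, while the hypothesis is worded for all subjects implanted. A failure before any follow-up film is outside the efficacy population altogether.

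The planned sensitivity analyses do not close the gap. Neither has a rule for failures. Imputation handles them as ordinary missing data, and LOCF carries a film taken before the revision past the revision itself. A subject whom 10.3 calls a failure can therefore appear as a 3-degree success. The safety summary in 9.2 is descriptive and does not feed into the efficacy result.

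**Working it through.** **Planning figure.** Inputs from 9.4.2: true change 5, null 3, SD 6, one-sided alpha 0.05, one-sample t. Noncentral t power is 0.898 at n = 78, 0.902 at n = 79 and 0.905 at n = 80. The stated 79 reproduces, and 79/0.8 rounds up to 99, against 100 enrolled. The sample size is not in dispute.

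**Assumptions for the rest.** Of 100 implanted subjects, 80 have known status at the primary visit (an observed value or a prior cage failure). The other 20 are missing for unrelated reasons. Let f be failures as a share of the 80, and v the change credited to a failure. Neither is in the documents, so f is set to 2%, 5% and 10%, and v to 0, -2 and +3. The others have SD 6.

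**Mean.** With the others at mean 5, the overstatement is 5 - [(1 - f) x 5 + f x v] = f x (5 - v).

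**False success.** If the mean over all known-status subjects is exactly 3, the observed subjects have mean (3 - f v)/(1 - f). Their number is 80(1 - f). The chance of passing the one-sided 5% test follows from the noncentral t.

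| v | Mean overstated (f = 2/5/10%) | False success (f = 2/5/10%) |
|---|---|---|
| 0 | 0.10 / 0.25 / 0.50 | 6.0% / 7.8% / 11.9% |
| -2 | 0.14 / 0.35 / 0.70 | 6.7% / 10.3% / 19.3% |
| +3 | 0.04 / 0.10 / 0.20 | 5.0% throughout |

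At v = 5 the mean is unbiased, and above 5 the bias reverses. For any v above 3 the observed mean under this null is below 3, so false success falls below 5%.

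**Simple 3-degree success.** P(change of 3 or more) with mean 5, SD 6 is Phi(2/6) = 63.1%. Counting failures as non-success gives 0.631 x (1 - f) = 61.8%/59.9%/56.8%. For example, with 4 failures among 80: 76 x 0.631 = 47.9, and 47.9/80 = 59.9%. If the failures instead sit within the 20% dropout, 5 of them beside 80 observed subjects give 80 x 0.631/85 = 59.3%. The 9.1.6 composite has two further conditions, and its rate cannot be computed from the documents.

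**LOCF.** If failures' last films average 5, 3 or 0 degrees (SD 6), LOCF scores 63%, 50% or 31% of declared failures as reaching 3 degrees. With the others at the planned mean of 5 and films also averaging 5, LOCF still reports 63.1%.

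False success is a separate scenario, with v = 0 and an overall mean of 3, so the others average 3/(1 - f) = 3.06/3.16/3.33:

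- Last films distributed like the others' values: 6.0%/7.9%/12.5%.
- Last films averaging 5: the LOCF mean is 3 + 5f = 3.10/3.25/3.50, and false success is about 7%/10%/18%.

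**A borderline result.** Observed mean 4.3, SD 6, n = 80 gives one-sided p = 0.028. Adding 5 failures at 0 gives mean 80 x 4.3/85 = 4.05, SD 5.91 and p = 0.053.

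**The case against.** The strongest reply is that direction and size are both assumed. The documents give no cage failure rate and no lordosis value for failures. A revision may follow infection or malposition, with no bearing on lordosis gain. At +3 there is no false-success inflation, and at 5 or more the mean bias vanishes or reverses. This stands, and it is why the figures are a range.

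A second reply is that lordosis while the original cage is in place is a reasonable quantity to estimate. It is, but the plan does not say so, and its hypothesis is worded for subjects implanted. Leaving the observed-data t-test as primary accommodates this view.

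A third reply is that the study is single-arm and post-market, and that a formal statistical analysis plan may settle the matter. The design does limit the weight of the point. However, 9.1.6 defers only the choice of literature sources to that plan.

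Some stronger readings are tempting but unsupported. A reader might infer that failing cages disappear from the efficacy analysis altogether. They do not: visits before the failure stay in the by-visit summaries, subjects with a film re-enter through imputation and LOCF, and cages that subside or collapse without revision, or are revised after the primary visit, keep their measured value. A reader might also infer that a confirmatory responder rate is inflated. The confirmatory test is on the mean, and the listed responder percentage is exploratory.

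**Conclusion.** The gap is real: followed as written, the plan leaves a declared failure out of the primary-visit result, or lets LOCF score it as a success. This holds whether the primary visit is at 12 months (Section 9) or 24 months (synopsis).

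Its size rests on the assumed failure rate and failure value. With no gain in failures it is small near 2%. It becomes material at 5-10%, where the mean is overstated by 0.25-0.50 degrees and false success is 7.8-11.9%; a loss in failures makes it larger. The documents do not support saying that the primary result will be biased, only that it is biased upward if failures gain less than the others. The change should be made because it is cheap and must be fixed before results are seen; it does not invalidate the primary test.

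**What to change.** Keep the observed-data t-test as primary, and amend 9.1.3, 9.3, 9.5 and the denominator rule as follows.

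- **(a) Responder summaries.** For the simple 3-degree success, count a cage revision or removal before the visit as non-success. The denominator is implanted subjects with an observed value or a prior failure, including failures before a first film, as a stated exception to 9.5. Subjects missing for other reasons are not added. Apply the same rule to the 9.1.6 composite only at visits where all its component images are scheduled. The Evaluation Schedule lists the long standing lateral only pre-operatively and at 1 year. If C7-S1 balance needs that film, the denominator at other visits would contain failures alone.
- **(b) Missing data.** Do not carry LOCF, or impute as ordinary missing data, across a cage revision or removal. In those analyses give failures one stated base value, for example 0. Add one sensitivity analysis of mean change that varies this value over a stated range with a neutral or favourable bound, for example -2 to +3, where +3 is neutral for the test.
- **(c) Reporting.** Tabulate cage failures by visit beside the efficacy results.

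No new data are needed, since 8.5 already requires surgical interventions on the eCRF. The cost is SAP wording, a few more outputs and a slightly less favourable responder percentage. The failure-inclusive mean analysis also has less power: about 88%/83%/73% at 2%/5%/10% failures with 0 gain and N = 80 (simulated, binomial number of failures), against the planned 90%.

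Three separate points also need reconciling, and add no weight here: the 12- versus 24-month primary visit; how a two-level subject is scored when the parameter is "Segmental lordosis (at each TLIF level in degrees"); and the meaning of reoperation, which 10.3 applies to revision of supplemental fixation while 8.5 limits it to procedures that change no component.

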### 8.1.2 Adverse Event Reporting Period

The study period during which AEs must be reported is normally defined as the period from the initiation of any study procedures to the end of the study treatment follow-up. The start of study procedures is considered to be the point of consent. Any AEs which fit the protocol defined reportable events must be reported from the time of consent until study completion.

At each contact with the subject the investigator must seek information on AEs by specific questioning and, as appropriate, by examination. Information on protocol defined AEs should be recorded immediately in the source document and also in the appropriate AE module of the CRF. All clearly related signs, symptoms and abnormal diagnostic procedure results should be recorded in the source document and grouped under one diagnosis, as appropriate. The clinical course of each event should be followed until resolution or until it is determined at the end of the study that the AE will not resolve.

CONFIDENTIAL

This material is the property of Stryker Spine. Do not disclose or use except as authorized in writing by Stryker.  
Page 22

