## 8.4 Recording of Adverse Events

All protocol defined AEs occurring during the study period must be recorded; this includes events that occur between scheduled visits. The clinical course of each event should be followed until resolution or stabilization.

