## 8.5 Surgical Interventions

Surgical interventions are classified separately from adverse events. All surgical interventions (defined below) must be recorded on the appropriate eCRF within five (5) business days and reported to Stryker Spine within forty-eight (48) hours.

Surgical interventions are defined as follows.

Revision - a procedure that adjusts or in any way modifies or removes **part** of the original implant configuration, with or without replacement of a component of the original configuration. This may include adjusting the position of the original configuration.

Removal - a procedure in which *all* of the original implant components are removed, with or without replacement.

Supplemental Fixation - a procedure in which additional instrumentation that is not part of the original configuration under study is implanted (e.g., supplemental placement of a rod/screw system or a plate/screw system).

Reoperation - any surgical procedure at the treated level that does not remove, modify, or add any components to the implant configuration (e.g., repair of dural leak). Reoperations unrelated to the spinal implants (e.g., treatment for wound infection, or surgical decompression for pre-existing leg (radicular) pain) are recorded as surgical interventions, but are not considered individual subject failures.

Any device removed during the course of the study is required to be returned to Stryker Spine for analysis.

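### Cage revision or removal ends the subject's study under Section 10.3, and no visible text provides for new adverse events, neurologic checks or questionnaires after the device has failed

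*Combined protocol and SAP*

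**What the plan says.** Section 10.3 gives the rule directly: "Revision or removal of the AccuLIF Cage System constitutes a failure and study termination for the subject". Its table of termination reasons includes removal of the study device and dates that termination to the day of the procedure; revision has no row of its own. For a subject discontinued by the center before the last evaluation, 10.3 adds that "the subject will be notified by the center that he/she is no longer in the study and a Study Termination CRF will be completed".

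Revision of the supplemental fixation is treated differently: "the event is considered a reoperation and does not constitute a failure or study termination".

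Section 8.5 defines a revision broadly as any procedure that modifies or removes part of the implant configuration, and notes: "This may include adjusting the position of the original configuration". It requires the intervention to be recorded and reported to the sponsor, and any removed device to be returned.

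On AEs, Section 8.1.2 says that reportable events "must be reported from the time of consent until study completion". An event is to be followed to resolution or "until it is determined at the end of the study that the AE will not resolve". Section 8.4 repeats the duty: "The clinical course of each event should be followed until resolution or stabilization".

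Neurologic status, VAS, ODI and SF-12 are collected at the visits in Sections 7.3 to 7.7. Section 9.6 puts everyone who has the operation in the safety population, and Section 9.2.2 summarises safety descriptively, by counts and percentages where these apply.

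**The concern.** Follow-up stops because the device failed, so what goes uncollected is selected by outcome. The secondary objectives in Section 2.2 include the occurrence of neurologic and other complications, and subjects with a failed cage are those whose later course bears most on that. A later infection, neurologic deficit or nonunion in such a subject would be a new event with no stated route into the data.

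The analysis does not make up for this. The subject remains in the safety denominator under 9.6, while 9.2.2 states no adjustment for follow-up time. An event that is not collected therefore counts as no event. The percentage of subjects with any AE should move little, because the AE that led to the revision normally counts the subject already. Event counts and percentages by type of event are what fall short.

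The protocol itself shows that follow-up after a second operation is workable, since it continues after a fixation revision.

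**Working it through.** **The plan's own figures.** The documents give no cage revision or removal rate, so there is no stated figure on this point to reproduce. The sample size in Section 9.4.2 is not in dispute: a one-sided one-sample t-test with a difference of 5 − 3 = 2 degrees, SD 6, alpha 0.05 and 90% power gives n = 79 (power 0.902). Then 79/(1 − 0.20) = 98.75, or 99, against 100 enrolled.

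**Step 1: what happens to each kind of data after cage revision or removal.**

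| Data | Relevant text | Position after termination |
|---|---|---|
| The procedure itself | 8.5 | Captured |
| The AE behind it | 8.1.1 (device, index procedure, lumbar spine, or serious) | Normally captured |
| AEs already open | 8.1.2, 8.4 | To be followed; 10.3 does not say how this works once the subject has left |
| New AEs | 8.1.2, 8.4, synopsis | No express provision; depends on the reading in Step 2 |
| Neurologic status, VAS, ODI, SF-12 | 7.3 to 7.7 | Tied to visits; no text extends the visits to terminated subjects |

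**Step 2: does new-AE reporting stop?** Section 8.1.2 runs reporting to study completion. If that means completion of the whole study, reporting continues. If it means the subject's own completion, it does not. Section 10.3 links completion to the individual subject's last evaluation: "When a subject completes the study according to protocol, including the final study evaluation, a Study Termination CRF will be completed". A terminated subject never reaches that evaluation, and 10.3 does not say what the phrase means for such a subject. Because 10.3 also says that a subject discontinued by the center is no longer in the study, stopping is the more natural reading. It is still an inference.

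**Step 3: size per failed subject, on that reading.** Inputs are 24 months of planned follow-up (synopsis) and five follow-up visits at 6 weeks and 3, 6, 12 and 24 months (Evaluation Schedule). I assume that termination takes effect at month t, the date of the procedure, and that a visit due at month t has been done. The protocol fixes that date for removal; for revision it is an assumption.

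Months lost = 24 − t. Share lost = (24 − t)/24. Visits lost = number of scheduled visits after t.

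| Failure at month t | Months of new-AE reporting lost | Share of 24 | Visits lost of 5 |
|---|---|---|---|
| 3 | 24 − 3 = 21 | 87.5% | 3 (months 6, 12, 24) |
| 6 | 24 − 6 = 18 | 75% | 2 (months 12, 24) |
| 12 | 24 − 12 = 12 | 50% | 1 (month 24) |

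The months are upper limits, because the other reading in Step 2 would keep AE reporting open. The visits do not depend on that phrase; they depend only on Section 7 not being extended to terminated subjects.

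**Step 4: cohort size.** With no revision rate, no rate of later complications and no post-failure scores in the documents, a cohort-level figure would rest wholly on outside assumptions. None is given.

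**The case against.** The strongest reply is that this is an openly stated design choice in a single-arm post-market study with descriptive safety reporting. After removal, symptoms and lumbar events reflect a second operation and perhaps another implant, so ending at device failure is defensible. For questionnaire scores this stands, and it is why they should not be pooled with the main summaries. It is a weaker reason to leave new AEs uncollected, since these subjects stay in the safety denominator.

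A second reply is that the text may already continue AE reporting. Section 8.1.2 can be read as running to the end of the whole study, Section 8.4 covers reportable AEs throughout the study period, and the synopsis has each subject followed for 24 months. This stands to the extent that the loss of AE reporting cannot be called certain. None of these places mentions a terminated subject, however, and 10.3 is the specific rule.

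A third reply is that existing capture is good. This stands too: the procedure, its cause and open AEs are covered. A reader who inferred that device failures vanish from the record would be wrong. Last observation carried forward (9.3) could also retain a pre-revision value, though that says nothing about the course after failure.

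A reader might further infer that every minor repositioning ends participation with the cage still in place. The 8.5 definition permits that reading, but 8.5 and 10.3 do not use their terms alike: 10.3 calls a fixation revision a reoperation, while 8.5 reserves that word for procedures that leave the components unmodified. The point does not depend on it.

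Finally, the case report forms, model consent and formal SAP are not in view and might address handling after termination.

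**Conclusion.** The point holds as a limited one. As written, Section 10.3 ends participation at cage revision or removal, and no visible text provides for new AEs, neurologic checks, VAS, ODI or SF-12 afterwards. Per failed subject the loss is up to 21, 18 or 12 of 24 months of new-AE reporting and 3, 2 or 1 of 5 visits, for failure at month 3, 6 or 12. The AE part assumes that reporting ends with the subject's termination, which is the more natural reading but not the only one. The consequence is incomplete event counts and percentages by event type in the safety population, and no outcome information after failure.

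A reader might infer that the rule flatters the mean ODI or other scores, or weakens the primary lordosis test. The documents support neither. They give no failure rate and no post-failure scores from which to size a shift in means, and the separate reporting proposed here would leave the main means as they are. The sample size allows for 20% dropout, and nothing in the documents shows that failures would exceed it.

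This is a change worth making because it is cheap and improves the safety information. It does not threaten the primary analysis.

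**What to change.** Amend Section 10.3 to say that cage revision or removal is recorded as a device failure but does not end data collection unless the subject withdraws consent. In the same place, state that:

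- AEs already open continue to be followed under 8.1.2 and 8.4;
- new reportable AEs are collected to month 24;
- the neurologic checks and questionnaires already scheduled go ahead.

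In Section 9.2.2, include post-failure AEs in the cumulative safety tables, flagged as occurring after revision or removal, and list all revisions and removals. Present post-failure VAS, ODI and SF-12 separately, because they also reflect the second operation.

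The cost is protocol wording, possibly a line in the consent form, and at most the 1 to 3 remaining scheduled visits for each subject who fails between months 3 and 12. No new type of assessment is needed.
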